7.4.1.1 Overall Survival

The distribution of OS will be estimated for each treatment arm using Kaplan-Meier methodology and compared between Arm A and Arm B using the log-rank test stratified by ECOG PS (0 and 1 combined versus 2), EGFR mutation type (exon 19 deletion or mutations in exon 21 [L858R]) and TKI chosen (erlotinib versus gefitinib). In addition, stratified Cox proportional hazard model will be used to estimate the hazard ratio and the corresponding 95% confidence interval.

Comparison of ASP8273 and erlotinib/gefitinib will be tested at 1-sided significance level of 0.025. The null hypothesis will be:

• H_{02} : OS of ASP8273 is not better than the comparator erlotinib/gefitinib

The accompanying alternative hypothesis is:

• H₁₂: OS of ASP8273 is better than the comparator erlotinib/gefitinib

OS will be evaluated on the FAS and PPS. Additional sensitivity analysis for OS will include:

• If there is a difference in the stratification values between IRT and the CRF, primary analysis may be repeated on the FAS using CRF stratification values

Table 5 OS Definition

Situation	Date of Event or Censor	Outcome
Death before analysis cutoff date	Date of death	Event
Death after analysis cutoff date	Analysis cutoff date	Censor
Last known alive is before cutoff date	Last known alive date	Censor
Last known alive is after cutoff date	Analysis cutoff date	Censor

OS = Date of Event or Censor – Date of Randomization +1

To investigate non-proportionality between the treatment arms, the analyses for PFS#1 by IRR will be carried out for OS.

Subsequent anti-cancer therapies will be collected and summarized by treatment arm within drug class. Imbalance in the use of subsequent anti-cancer therapy may potential bias the inference in OS. The following methods may be used to assess the impact of the use of subsequent anti-cancer therapy in OS.

 Censor OS at the last contact date prior to the initiation of subsequent anti-cancer therapy

- Rank-preserving structural failure time method (RPSFT) to correct for confounding introduced by the change of treatment. The RPSFT model is based on an accelerated failure time model and uses a structural assumption of time-proportionality instead of a proportional hazards assumption as used in the Cox model
- Inverse probability of censoring weights (IPCW).

7.4.1.2 Objective Response Rate

The comparison of ORR without confirmation as assessed by the blinded IRR between Arm A and Arm B will be performed using stratified CMH test. In addition, ORR for each arm will be estimated and corresponding 95% confidence interval will be constructed.

ORR will be assessed on the FAS.

Comparison of ASP8273 and erlotinib/gefitinib will be tested at 1-sided significance level of 0.025. The null hypothesis will be:

• H_{03} : ORR of ASP8273 is not better than the comparator erlotinib/gefitinib

The accompanying alternative hypothesis is:

• H₁₃: ORR of ASP8273 is better than the comparator erlotinib/gefitinib

Sensitivity analyses for ORR include:

- Repeat the analysis on the PPS.
- Repeat the analysis for ORR with confirmation as assessed by the blinded IRR
- Repeat the analysis for ORR without confirmation as assessed by the local investigator

7.4.1.3 Disease Control Rate

The comparison of DCR without confirmation as assessed by the blinded IRR between Arm A and Arm B will be performed using stratified CMH test. In addition, DCR for each arm will be estimated and corresponding 95% confidence interval will be constructed.

DCR will be assessed on the FAS.

Sensitivity analyses for DCR include:

- Repeat the analysis on the PPS.
- Repeat the analysis for DCR with confirmation as assessed by the blinded IRR
- Repeat the analysis for DCR without confirmation as assessed by the local investigator

7.4.1.4 PFS#1 by local investigator

The distribution of PFS#1 by local investigator will be estimated on the FAS for each treatment arm using Kaplan-Meier methodology and compared between Arm A and Arm B using stratified log-rank test as specified in [Section 7.4.1]. In addition, stratified Cox

Sponsor: Astellas Pharma Global Development, Inc.

ISN/Protocol 8273-CL-0302

proportional hazard model will be used to estimate the hazard ratio and the corresponding 95% confidence interval.

7.4.1.5 **Duration of Response**

The distribution of DOR will be estimated on the FAS for each treatment arm using Kaplan-Meier methodology and compared between Arm A and Arm B using stratified log-rank test as specified in [Section 7.4.1]. In addition, stratified Cox proportional hazard model will be used to estimate the hazard ratio and the corresponding 95% confidence interval.

Table 6 DOR Definition

Situation	Date of Event or Censor	Outcome				
Subject with CR or PR (no confirmation required):						
Radiographical progression documented per	Date of radiological PD	Event				
RECIST v1.1						
No radiographical progression	Date of last radiological	Censor				
	assessment or at the date of					
	first CR or PR if no post-					
	baseline radiological					
	assessment is available					

DOR = Date of Event or Censor – Date of first CR or PR +1

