The Full Analysis Set (FAS) will be used for the primary efficacy analysis. All subjects who are randomized will be included in the FAS. For time to event endpoints including PFS, OS and DOR, log-rank test stratified by ECOG PS (0 and 1 combined versus 2), EGFR mutation status (exon 19 deletion or mutations in exon 21 [L858R]), TKI chosen (erlotinib versus gefitinib) will be used to compare the 2 treatment arms. The hazard ratio and corresponding 95% confidence interval from the stratified Cox proportional hazards regression model will also be presented. The median survival function will be estimated using the Kaplan-Meier method and will be reported along with the corresponding 95% confidence interval by treatment arm.

ORR and DCR will be compared between treatment arms using Cochran-Mantel-Haenszel test, stratified by the same stratification factors used in time to event analyses. The difference in response rates between the treatment arms will be estimated along with the corresponding 95% confidence interval.

Hochberg procedure will be used to control the overall error rate at 1-sided 0.025 level for secondary efficacy endpoints (OS and ORR). Only when the primary endpoint significantly favors the ASP8273 arm will secondary endpoints be tested.

Pharmacokinetics:

Descriptive statistics (e.g., N, mean, standard deviation, minimum, median, maximum, coefficient of variation and geometric mean) will be provided for plasma concentrations of ASP8273 and its metabolite(s) (if applicable) at each visit. Additional model-based analyses may be performed and reported separately.

Interim Analyses:

An interim futility analysis is planned to occur after at least 210 PFS events are observed, which is expected approximately 22 months after the first subject is randomized. If the observed HR at the

interim is larger than 1.1, recruitment into the study may be stopped at the interim analysis. Otherwise, recruitment into the study will continue as planned until 600 subjects are recruited. The interim analysis will be conducted by the IDMC. In addition safety data reviews during the trial will be conducted by the IDMC on a periodic basis. For example, the IDMC will review safety data after the first 50 subjects have been randomized and on study drug for approximately 3 months. The full procedures for IDMC safety review will be described in a separate IDMC charter.

V. FLOW CHART AND SCHEDULE OF ASSESSMENTS

Flow Chart

[figure not shown]

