7.4.2.5 Duration of Response (DOR)

DOR is defined as the time from the date of the first response CR/PR (whichever is first recorded) as assessed by IRR to the date of radiographic progression or date of censoring. If a subject has not progressed, the subject will be censored at the date of last radiological assessment or at the date of first CR/PR if no post-baseline radiological assessment is available.

The distribution of DOR will be estimated for each treatment arm using Kaplan-Meier methodology and compared between Arm A and Arm B using the log-rank test stratified by ECOG PS (0 and 1 combined versus 2), EGFR mutation type (exon 19 deletion or mutations in exon 21 [L858R]) and TKI chosen (erlotinib versus gefitinib). In addition, stratified Cox proportional hazard model will be used to estimate the hazard ratio and the corresponding 95% confidence interval.

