5.1 Full Analysis Set (FAS)

The full analysis set will consist of all subjects who are randomized. This will be the primary analysis set for efficacy analyses.

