6.1.2.4 Duration of Response (DOR)

DOR is defined as the time from the date of the first response CR/PR (whichever is first recorded) as assessed by IRR to the date of radiographical progression or date of censoring. If a subject has not progressed, the subject will be censored at the date of last radiological assessment or at the date of first CR/PR if no post-baseline radiological assessment is

available. DOR will be derived for subjects with best overall response as CR or PR (without confirmation).

DOR (in days) is calculated as:

(Date of documented progression or censoring) – (Date of the first response CR/PR) +1.

To apply the cut-off date to DOR is to exclude tumor assessments after cut-off date in the analysis.

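### Duration of response is compared between arms by log-rank test and hazard ratio although it exists only for responders; it should be labelled descriptive, with any comparison made over all randomized subjects

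*SAP*

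**What the plan says.** SAP 7.4.1.5 states "The distribution of DOR will be estimated on the FAS for each treatment arm". It compares the arms with the stratified log-rank test used for PFS, and adds that a "stratified Cox proportional hazard model will be used to estimate the hazard ratio and the corresponding 95% confidence interval". SAP 5.1 defines the set named there: "The full analysis set will consist of all subjects who are randomized".

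The variable itself is narrower. SAP 6.1.2.4 says "DOR will be derived for subjects with best overall response as CR or PR", without confirmation. Table 6 of the SAP lists only subjects with CR or PR. The duration formula starts at the date of first response, and no rule covers a subject who never responds.

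The protocol plans the same comparison. In Protocol 7.4.2.5 DOR is "compared between Arm A and Arm B using the log-rank test stratified by" ECOG status, mutation type and TKI chosen. The synopsis groups it with the other time-to-event endpoints: "For time to event endpoints including PFS, OS and DOR, log-rank test stratified by ECOG PS".

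Two further sections set the status of the result. SAP 7.1 makes every comparison one-sided at 0.025, with superiority of Arm A as the alternative, unless stated otherwise; nothing is stated otherwise for DOR. SAP 7.4.1 restricts the Hochberg procedure to OS and ORR, gated on PFS, so DOR lies outside the controlled family.

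**The concern.** Randomization makes the two arms comparable. It does not make the responders in one arm comparable with the responders in the other, because response is itself an effect of treatment. If ASP8273 produces responses in subjects who would not have responded to erlotinib or gefitinib, its responder group contains a kind of subject that is absent from the control responder group. Stratifying on three baseline factors does not repair this.

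The SAP tests superiority on ORR (7.4.1.2), so the plan itself anticipates a difference in response rates. The better ASP8273 does on ORR, the harder the DOR hazard ratio is to interpret. The SAP recognises a comparable problem for OS, where it warns about subsequent therapy and lists methods to assess it, and it labels the QoL analyses descriptive. DOR has neither a warning nor a label. Amendment 1 made it a secondary endpoint on the ground that it is clinically important, so its hazard ratio and p-value will be read.

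**Working it through.** **The plan's own figures.** Neither document gives a planning ORR or DOR, so there is no DOR figure to reproduce. The only planning figure is PFS power: Φ(√420 × |ln 0.667|/2 − 1.96) = Φ(20.49 × 0.2025 − 1.96) = Φ(2.19) = 98.6%, in line with the protocol's 98.7%. Every input below is an assumption.

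**Illustration 1: extra, short-lived responders.** Assume 60% of subjects would respond on either drug, with exponential durations and medians of 12 months (ASP8273) and 10 months (control). The true hazard ratio in these subjects is 10/12 = 0.83. A further share *x* responds only on ASP8273, with median 4 months.

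For *x* = 10%, the weights among Arm A responders are 0.60/0.70 = 0.857 and 0.10/0.70 = 0.143. The Arm A curve is S(t) = 0.857 × 2^(−t/12) + 0.143 × 2^(−t/4).

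- Median: S(10.2) = 0.476 + 0.024 = 0.50, so 10.2 months against 10.0.
- Hazard ratio at the start of response: (0.857/12 + 0.143/4)/(1/10) = 1.07. It falls towards 0.83 as the short-lived responses end.
- Cox hazard ratio (large-sample solution of the score equation): 0.925 without censoring and 0.95 with censoring. Censoring here assumes uniform accrual over 22 months, cut-off at month 36 and response at month 2. It gives more weight to the early period, which raises the estimate.

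For *x* = 15%, the weights are 0.80 and 0.20. The median is 9.5 months against 10.0, the starting hazard ratio is (0.80/12 + 0.20/4)/(1/10) = 1.17, and the Cox hazard ratio is 0.966 without censoring and 1.00 with it.

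**The same illustration over all randomized subjects.** Mean months in response, truncated 24 months after first response and counting non-responders as zero, uses m_k = (k/ln 2)(1 − 2^(−24/k)) for median k. This gives m_12 = 12.98, m_10 = 11.69 and m_4 = 5.68.

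- Control: 0.60 × 11.69 = 7.0 months.
- ASP8273, *x* = 10%: 0.60 × 12.98 + 0.10 × 5.68 = 7.79 + 0.57 = 8.4 months.
- ASP8273, *x* = 15%: 7.79 + 0.85 = 8.6 months.

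The 10% gain of 1.3 months is about 0.8 from longer response in the common responders and 0.6 from the extra responders (rounded).

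**Illustration 2: trial-sized simulation.** There were 1,000 trials per row, with 300 subjects per arm and the same accrual, cut-off and response time. Tests were unstratified. Control medians from month 2 were 12 months in subjects who respond on either drug (11 in row 1) and 4 months in all others.

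| Assumed truth | ORR, A vs B | PFS HR (power) | DOR HR (power) |
|---|---|---|---|
| HR 0.667 in every group, same responders | 70% vs 70% | 0.70 (97%) | 0.67 (93%) |
| HR 0.667 in every group | 70% vs 60% | 0.71 (95%) | 0.78 (54%) |
| HR 0.667 in every group | 80% vs 60% | 0.70 (97%) | 0.86 (24%) |
| HR 0.35 in added responders only | 80% vs 60% | 0.84 (48%) | 1.02 (2%) |
| No effect on time to progression | 80% vs 60% | 1.00 (2%) | 1.26 (0%) |

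In the last row the DOR log-rank is significant against ASP8273 at one-sided 0.025 in 52% of trials. Exchanging the arm labels gives 1/1.26 = 0.79: a drug with fewer but better-prognosis responders would look better on DOR with no effect on progression. The first row shows that the distortion disappears when the responder sets are the same.

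**The case against.** Four objections carry weight.

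- *The FAS wording.* A reader might infer that naming the FAS is a substantive error. Read with SAP 6.1.2.4 and Table 6, it most naturally means responders within the FAS rather than the PPS. A non-responder has no start date and cannot enter the formula. This is a wording point only, but the natural reading leaves the selection problem in place.
- *Formality of the test.* A reader might infer that DOR is a confirmatory test that threatens error control. The documents do not support that. OS and ORR have stated null and alternative hypotheses; DOR has none, and it is outside the Hochberg family. Its p-value is nominal, and it is a test only through the default in SAP 7.1.
- *A hidden benefit.* A reader might infer that the trial could miss a real benefit. Extra responses and later progression are already compared over all randomized subjects through ORR and PFS. In rows 2 and 3 of the table PFS power is 95% and 97% while DOR is diluted. In row 4 PFS power is low because the overall PFS effect is weak, not because of how DOR is analysed.
- *Assumed size.* The split between subjects who respond on either drug and those who respond on one only cannot be observed. Illustration 1 shows dilution of the hazard ratio to at most 1.00, not reversal; only the median in the 15% case falls below control. Values above 1 need the different assumptions of rows 4 and 5.

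What remains is that a between-arm hazard ratio and p-value on a post-randomization subset are planned in three places without any statement of how to read them.

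**Conclusion.** The point stands as a moderate one about a secondary endpoint. As planned, the DOR hazard ratio is a treatment effect only if the responders in the two arms are comparable, and the plan's ORR hypothesis anticipates that they may not be. Under the assumed 10 to 15% of extra responders with a 4-month median, a true 0.83 becomes about 0.92 to 0.97, or 0.95 to 1.00 with the assumed censoring. Other assumptions give larger or opposite distortions, and identical responder sets give none. The direction in this trial cannot be predicted from the documents. The principle is firm; the size is illustrative. The primary PFS conclusion and the controlled OS and ORR conclusions do not depend on DOR.

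**What to change.** In SAP 7.4.1.5, Protocol 7.4.2.5 and the synopsis efficacy paragraph:

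1. Name the population as responders in the FAS.
2. Report Kaplan-Meier medians with 95% confidence intervals by arm, labelled descriptive.
3. Give no inferential p-value or hazard ratio for DOR. If one is shown, label it descriptive and not for inference, and state that it is an exception to the default in SAP 7.1.
4. If a between-arm comparison is wanted, use restricted mean time in response over all randomized subjects, with zero for non-responders and a prespecified truncation time. The 36 months already used for PFS RMST is one option. Because the primary analysis is expected about 36 months after the first randomization, the largest time that follow-up supports may be shorter. State that this measure combines response rate and duration, so it answers a different question from DOR.

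The cost is wording in two documents, one small additional analysis from data already collected, and the loss of a nominal p-value.

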7.4.2 Analysis of Exploratory Endpoint

7.4.2.1 PFS#2

The distribution of PFS#2 will be estimated on the FAS for each treatment arm using Kaplan-Meier methodology and compared between Arm A and Arm B using stratified log-rank test as specified in [Section 7.4.1]. In addition, stratified Cox proportional hazard model will be used to estimate the hazard ratio and the corresponding 95% confidence interval.

Table 7 PFS#2 Definition

Situation	Date of Event or Censor	Outcome
Subject did not receive new anti-cancer	Day 1	Censor
therapy		
Subject received new anti-cancer therapy:		
Subject has investigator-determined	Minimum of [Date of	Event
progression on that treatment or ended that	investigator determined PD, date	
treatment or started another therapy or death	of death, new ACT end date, or	
	start date of another therapy]	
Subject did not die nor progressed nor	Last known alive date	Censor
stopped the new ACT nor started another		
therapy at the time of analysis cutoff date		

PFS#2 = Date of Event or Censor – Date of initiation of new systemic anti-cancer treatment +1

7.4.3 QoL/PRO

Descriptive QoL and PRO analyses will be performed on the FAS. Completion rate for each questionnaire will be summarized. Additional analyses will be discussed in details in a separate PRO SAP.

7.4.3.1 FACT-EGFRI-18

Means and standard deviations and change from baseline at each scheduled assessment will be reported for each of the FACT-EGFRI-18 domains (physical, social/emotional and functional well-being). The analyses will include data from the baseline assessment through the last available data.

Detailed scoring instructions for these domains are provided in Appendix 10.3 All time point data will be included and summarized.

7.4.3.2 EORTC-QLQ-C30

Means and standard deviations and change from baseline at each scheduled assessment will be reported for each of the QLQ-C30 subscales. The analyses will include data from the baseline assessment through the last available data.

Detailed scoring instructions for these scales are provided in Appendix 10.5 All time point data will be included and summarized.

7.4.3.3 EORTC-QLQ-LC13

Means and standard deviations and change from baseline at each scheduled assessment will be reported for each of the QLQ-LC13 subscales. The analyses will include data from the baseline assessment through the last available data.

Detailed scoring instructions for these scales are provided in Appendix 10.4 All time point data will be included and summarized.

7.4.3.4 EQ-5D-5L

Descriptive characteristics of EQ-5D-5L will be summarized from baseline assessment through the last available data. Frequency and the percentage of reported problems for each level for each dimension will be provided. Shift table showing shift in each dimension score from baseline to each post-baseline visit will be provided for the 5 dimensions (mobility, self-care, usual activities, pain/discomfort and anxiety/depression). 2D bar plots will be generated to summarize the reported problems for each level for each dimension.

EQ-5D-5L VAS will be summarized by treatment group at each visit using descriptive statistics (mean, standard deviation, minimum, maximum and median). Additionally, a within-subject change will be calculated as the post-baseline score minus the baseline score and summarized in the same way. ANOVA model will be used to evaluate change from baseline to post-baseline visits for the EQ-5D-5L VAS including treatment as a fixed factor, and baseline score as a covariate.

Detailed scoring instructions for these dimensions are provided in Appendix 10.6 All time point data will be included and summarized.

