If a subject discontinues study drug prior to radiographic disease progression (i.e., PFS#1), the subject should continue to undergo imaging assessment (including brain imaging when indicated and collection of tumor measurements) every 56 days (±7 days) in the posttreatment follow-up period until PFS#1 is documented per the investigator, the subject misses 2 or more consecutive scheduled tumor assessments, or the subject starts another cancer treatment, whichever occurs earlier.

After PFS#1, subjects will be followed in the long-term follow-up period per institutional guidelines, but not less frequently than every 3 months to confirm survival status and collect subsequent anticancer treatment details and progression status until PFS#2 is documented or the subject starts another cancer treatment, whichever occurs earlier. Phone contact with subject is sufficient for follow-up. Additional follow-up contacts may be required per sponsor request for analysis purposes.

³ Quality of life (EQ-5D-5L only) will be assessed at each of the posttreatment or long-term follow-up survival contacts for 6 months after treatment discontinuation. QoL may be assessed by telephone module if follow-up contact is done by phone.

⁴ Subjects will be followed via phone call in the survival follow-up period approximately every 3 months to collect survival status until subject death or study closure. Additional follow-up contacts may be required per sponsor request for analysis purposes.

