6.5 Quality of Life Variables

Subjects will be asked to complete the QoL and PRO questionnaires electronically at baseline and at day 1 of each cycle where a visit takes place.

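### The SAP's one PRO model, for EQ-5D-5L VAS change, has no visit or subject term and does not say whether visits are pooled; a repeated-measures model would be better and cheap

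*SAP*

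**What the plan says.** SAP 7.4.3.4 gives the model in one sentence: "ANOVA model will be used to evaluate change from baseline to post-baseline visits for the EQ-5D-5L VAS including treatment as a fixed factor", to which it adds the baseline score as a covariate. It is therefore an ANCOVA, though called an ANOVA. Visits are plural, and no target visit, visit effect, subject effect or covariance structure is given.

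The outcome is repeated. SAP 6.5 has the questionnaires completed at baseline and "at day 1 of each cycle where a visit takes place". By SAP Table 1 and section 3.2.1 that means day 1 of cycles 2 to 7 and of odd cycles from 9, plus the end-of-treatment visit. SAP Table 2 adds the 30-day follow-up visit and, for the EQ-5D-5L alone, the "posttreatment or long-term follow-up survival contacts for 6 months after treatment discontinuation", by telephone if needed.

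The other instruments are descriptive. For the QLQ-C30 the SAP says "Means and standard deviations and change from baseline at each scheduled assessment will be reported for each of the QLQ-C30 subscales", and it treats FACT-EGFRI-18 and QLQ-LC13 in the same way. SAP 7.4.3 then says "Additional analyses will be discussed in details in a separate PRO SAP".

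Three general rules bear on the point. Comparisons are one-sided at 0.025 unless stated otherwise (SAP 7.1). By-visit summaries use nominal visits (SAP 7.10.3). Missing data are not imputed as a general principle (Protocol 7.10).

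**The concern.** A model with only treatment and baseline score suits one outcome per subject. Here each subject contributes several.

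If all visits go into one fit, scores from the same subject are treated as independent and the treatment standard error is too small. If the model is fitted visit by visit, that problem goes. But each comparison then rests only on subjects with a score at that visit and makes no use of what was recorded for those who have left.

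The text does not choose between the two. The choice is left to programming in an open-label trial, for an endpoint that Amendment 1 moved from exploratory to secondary. At stake is the credibility of the only PRO comparison that this SAP models.

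**Working it through.** **Plan's figures.** The documents give no SD, effect size, correlation or power for the VAS. The design inputs that bear on attendance are median PFS of 15.6 and 10.4 months (Protocol 7.1). They are consistent with the stated HR: 10.4/15.6 = 0.667. Power with 420 events is Φ(√420/2 × |ln 0.667| − 1.96) = Φ(2.19) = 98.6%, against 98.7% in Protocol 7.1. SAP section 4 gives 95% for the same inputs; that is a separate discrepancy and does not affect this point.

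**Scores per subject.** Cycles 2 to 7, 9, 11 and 13 give nine post-baseline visits by cycle 13. Assume exponential PFS at the design medians and treatment ending at the PFS event. Summing the share still on treatment over those visits gives 7.2 scores per subject in Arm A and 6.5 in Arm B. A range of k = 5 to 8 is reasonable.

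**Pooled reading.** Treatment varies only between subjects, so the true SE is the naive SE times √(1 + (k − 1)r), where r is the within-subject correlation left after baseline adjustment. Under compound symmetry with raw correlation ρ, r = (ρ − ρ²)/(1 − ρ²) = ρ/(1 + ρ). The values of ρ are assumed.

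| k | ρ | r | SE ratio | True one-sided level, 1 − Φ(1.96/ratio) |
|---|---|---|---|---|
| 5 | 0.4 | 0.29 | √(1 + 4 × 0.286) = 1.46 | 0.09 |
| 8 | 0.6 | 0.375 | √(1 + 7 × 0.375) = 1.90 | 0.15 |

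A simulation agrees: 300 per arm, nine visits to cycle 13, no true VAS effect, equal PFS, dropout unrelated to health, 1,500 runs. With r = 0.3, the pooled model rejected 26% of the time at nominal two-sided 5%.

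**By-visit reading.** Progression-free at time t is 2^(−t/median).

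- 12 months: 2^(−12/15.6) = 59% in Arm A; 2^(−12/10.4) = 45% in Arm B.
- Cycle 13 day 1 (336 days, 11.0 months): 61% vs 48%, about 184 vs 144 of 300.

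These are progression-free shares, not attendance. If EQ-5D-5L collection ran a full 6 months past each PFS event, the share inside the collection window at 12 months would be at most the share progression-free at 6 months: 2^(−6/15.6) = 77% and 2^(−6/10.4) = 67%. This bound counts deaths as still in the window.

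The same simulation gives the by-visit test at cycle 13, again with no true effect:

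| PFS | Dropout linked to health | Two-sided rejection at nominal 5% | Mean spurious difference |
|---|---|---|---|
| Design medians | No | 4.3% to 5.7% | about 0 |
| Design medians | Yes (assumed) | 7.7% to 12.9% | 0.05 to 0.09 SD against Arm A |
| Equal in both arms | Yes (assumed) | 4.4% to 6.0% | about 0 |

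Ranges cover residual correlations of 0.3 to 0.7. The lower end is the relevant one after baseline adjustment; under compound symmetry r cannot exceed 0.5.

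**The case against.** The best defence is that the model is meant by visit. The sentences just before it in SAP 7.4.3.4 summarise the VAS and its change at each visit, and SAP 7.10.3 relies on nominal visits. That is the more natural reading, and under it the SE problem does not arise. It is not certain: the section refers to visits in the plural, ends by saying that all time points are included, and never says that fits are separate.

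A reader might go further than the documents allow in four ways.

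- **That this is the trial's only PRO comparison.** It is the only one modelled in this SAP. The PRO SAP may hold a longitudinal model. But additional analyses do not withdraw the one stated here.
- **That the pooled level is 0.11 to 0.20.** Putting the raw correlation straight into the SE formula gives ratios of 1.61 to 2.28 and those levels. The model adjusts for baseline, which lowers the correlation that matters, so 0.09 to 0.15 is the fair range.
- **That 59% vs 45% is who answers at 12 months.** EQ-5D-5L collection goes on for 6 months off treatment, and Protocol 6.1 lets some subjects stay on drug after investigator-assessed progression. The SAP does not say whether off-treatment contacts enter the model.
- **That unequal attendance is itself bias.** It is not. Bias needs dropout that is related to health and differs by arm. The inequality comes from the design HR and disappears if PFS is equal. In the simulated case the bias ran against Arm A, so with one-sided tests it would hide a benefit rather than create a false claim for ASP8273.

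It also stands that SAP 7.4.3 plans the PRO analyses as descriptive, with completion rates reported, and that no VAS hypothesis is stated.

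**Conclusion.** The point holds as a worthwhile improvement to the SAP. The stated model does not fit a repeated outcome, and the text does not settle how it is to be applied.

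Pooled, the treatment SE is understated about 1.5- to 1.9-fold and the true one-sided level is about 0.09 to 0.15. This rests on 5 to 8 scores per subject, an assumed raw correlation of 0.4 to 0.6 and compound symmetry.

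By visit, the error rate is sound when dropout is unrelated to health. The certain loss is the unused earlier data from subjects who have left. Bias is conditional, and its size depends on an assumed link that the documents do not quantify.

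A reader might infer that a main efficacy claim is at risk. It is not: the Hochberg family in SAP 7.4.1 contains only OS and ORR, so primary and key secondary conclusions do not change.

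**What to change.** Replace the ANOVA sentence in SAP 7.4.3.4 with a mixed model for repeated measures:

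- **Outcome and visits:** VAS change from baseline at a named list of scheduled on-treatment visits, for example day 1 of cycles 2 to 7, 9, 11 and 13.
- **Terms:** treatment, visit, treatment-by-visit, baseline VAS, baseline-by-visit, and the stratification factors of the primary analysis (ECOG PS 0 and 1 versus 2, EGFR mutation type, TKI chosen).
- **Covariance:** unstructured within subject, with a fallback stated in advance if the model does not converge.
- **Reporting:** treatment difference with confidence interval at each named visit.
- **Off-treatment scores:** say whether the end-of-treatment, follow-up and later contacts enter the model. If they do, give the rule that maps them to visits.
- **PRO SAP:** state the same model there.

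The cost is SAP wording and a little more programming with a standard SAS procedure. The model relies on data being missing at random. It uses the earlier scores of subjects who leave, but it does not resolve dropout through death or through decline that was never recorded, and the SAP should say so.
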